## **PROTOCOL SYNOPSIS**

TITLE	Evaluation of the impact of fascial closure technique on post- operative pain in patients undergoing Pfannenstiel incision for Caesarean Section: A Randomised Trial
SPONSOR	DAN Women and Babies Unit, Sunnybrook Health Sciences Centre
FUNDING	DAN Women and Babies Unit, Sunnybrook Health Sciences Centre
ORGANISATION	
NUMBER OF SITES	1
RATIONALE	Caesarean sections are the most commonly performed surgical procedure throughout the world. Within the Canadian population, approximately one-third of all deliveries occur via Caesarean section. Chronic pain post-operatively has been identified as an issue that a large proportion of patients suffer with. As a result, a variety of surgical techniques have been undertaken, with some being compared to ascertain the reason for this chronic pain. One method which has been observed is related to the fascial layer and associated pain related to this layer. Whilst the abdominal fascia plays an integral role in ensuring the abdominal contents remain in situ. A variety of methods have been employed and studied to ensure the integrity of the fascial layer to reduce the risk of dehiscence, but no studies undertaken to date have evaluated the method of fascial closure and their effect on post-operative pain.
STUDY DESIGN	Randomised, double-blind, three-arm trial
PRIMARY OBJECTIVES	1. Analgesia use
	2. Pain score between three groups
NUMBER OF SUBJECTS	350
SUBJECT SELECTION	Inclusion Criteria:
	- Women aged 18-60 years
	- Women with singleton pregnancy
	
 
Patient undergoing elective lower segment Caesarean section via a Pfannenstiel Incision
 

	- Use of Regional Anaesthesia (epidural or spinal anaesthesia)
	Exclusion Criteria:
	- Multiple pregnancy
	
 
Patient undergoing non-elective Caesarean section
 

	- Caesarean section through midline laparotomy incision
	
 
Patients undergoing Caesarean section under General Anaesthesia
 

	- History of chronic pain
	
 
History of chronic pain
 
History of post-operative complications (haematoma, abscess,
 

	- History of post-operative complications (naematoma, abscess, dehiscence, re-operation)

	· · · · · · · · · · · · · · · · · · ·									
ARMS AND	Participants will be blinded to which method of fascial closure will									
INTERVENTIONS	be undertaken at the time of their surgery.									
	1. Single suture, knot above rectus fascia									

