	2. Two sutures, knots above rectus fascia									
	3. Two sutures, buried knots below rectus fascia									
DURATION OF SUBJECT	Subjects will be enrolled in the study for 10 weeks.									
PARTICIPATION AND	Screening: 1 day									
DURATION OF STUDY	Treatment: 1-2 days (subjects will be admitted to hospital)									
	Follow-up: 10 weeks									
	The total duration of subject recruitment time is 6 months, with									
	subsequent follow-up over a 10-week period after initial									
	recruitment.									
EFFICACY										
EVALUATIONS										
PRIMARY ENDPOINT	1. Analgesia use in first 72-hour period post-operatively.									
	2. Pain score questionnaire results over 10-week post-operative									
	period.									
STATISTICS										
Primary Analysis Plan	Statistical analysis will be undertaken using IMB ® SPSS ® Statistical									
	Software ver. 26 to undertake a two-sided T-test comparing group									
	1 vs. 2 and group 1 vs. 3 to assess for statistical significance in									
	analgesia use and pain scores.									
Rationale for Number	Based on a power of 80% at an alpha of 0.05, we estimate a 15%									
of Subjects	reduction in pain scores. As a result, we require a total of 255									
	subjects in this study. Given an estimated drop-out rate of 35%, we									
	aim to recruit a total of 350 participants.									
	In addition, sub-group analysis will be undertaken comparing pain									
	scores between primary and repeat Caesarean sections. Based on									
	the same power of 80% at an alpha of 0.05, with an estimation of a									
	15% difference in pain scores, we require a total of 140 subjects for									
	this sub-group analysis.									
L										

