### 2.1 Hypothesis

Our study hypothesises that the presence of a thicker knot in the subcutaneous layer when closing the rectus fascia leads to more irritation of the cutaneous nerves causing more sensitivity and perceived pain by the patient. In addition, we also hypothesise that by burying the knot under the rectus fascia at the angle of the rectus incisions will further diminish the level of nerve irritation in the subcutaneous layer and will allow for a further reduction in perceived pain and analgesia requirements.

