#### **10.2 Statistical Analysis**

For our primary outcome measure, we aim to perform statistical analysis using IBM® SPSS® Version. 26 Statistics Software for Windows to perform a two-sided T-test whereby comparing groups directly. Based upon an 80% power at an alpha of 0.05, we anticipate a 15% when comparing group 1 vs 2 and group 1 vs 3, we require a sample size of 255 participants across all three groups.

Specific to our subgroup analysis evaluating primary vs. repeat caesarean section, based upon an 80% power at an alpha of 0.05, we anticipate a 15% difference in comparing these two groups using a two-sided T-test. As a result, we require a sample size of 140 participants across these two groups.

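### The primary tests have no success or error rule, the number of primary endpoints is unclear, and arm 2 vs arm 3, which tests the buried knot, is never named

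*Combined protocol and SAP*

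**What the plan says.** **Endpoints.** The synopsis lists two primary endpoints: "Analgesia use in first 72-hour period post-operatively" and "Pain score questionnaire results over 10-week post-operative" (the sentence continues to the word period). Its primary objectives are also two, analgesia use and "Pain score between three groups". Section 10.2, however, opens with "For our primary outcome measure, we aim to perform statistical analysis", in the singular. The synopsis rationale for the number of subjects bases the 15% on pain scores only and gives no effect size for analgesia use. Section 3.1 states the objective as evaluating pain, then mentions both pain scores and analgesic requirements as what the questionnaire captures.

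**Tests.** The synopsis analysis plan specifies two-sided t-tests of group "1 vs. 2 and group 1 vs. 3 to assess for statistical significance in" analgesia use and pain scores. In section 10.2 the analysis sentence says only "to perform a two-sided T-test whereby comparing groups directly"; the two pairs appear in the sizing sentence that follows, "at an alpha of 0.05, we anticipate a 15% when comparing group 1 vs 2 and group 1 vs 3". The explicit restriction to two pairs therefore rests mainly on the synopsis.

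**Error level.** The synopsis, section 5.2 and section 10.2 each give alpha 0.05 in the sizing text. None gives a level per test, an order of endpoints or a success criterion. Section 10 promises a detailed SAP before the final analysis; the text supplied contains no such rule.

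**Hypothesis and arms.** Section 2.1 predicts that burying the knot "will allow for a further reduction in perceived pain and analgesia requirements". As section 6 describes them, arm 1 uses one suture. Arms 2 and 3 each use two, run and joined in the same way, and differ in whether the angle knots lie above or below the rectus fascia.

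**The concern.** There are two separate gaps.

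First, two endpoints by two contrasts make four primary tests, with no statement of how many must be significant, or which. If this stays open until the results are known, a significant result on either endpoint and either contrast could be reported as the primary success, and the nominal 5% would no longer describe the chance of a false claim.

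Second, the buried-knot hypothesis has no named test. Arm 3 differs from arm 1 in both number of sutures and knot position, so a significant 1 vs 3 could not be attributed to burying the knot. The contrast that holds suture number fixed is 2 vs 3.

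**Working it through.** **Inputs from the documents.** Alpha 0.05, two-sided t-test, 80% power, 85 per arm (sections 5.2 and 10.2); two listed endpoints and two listed contrasts (synopsis); recruitment of 350 with 35% drop-out (section 5.2). No SD or control mean is given.

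**The plan's own figure.** 85 per arm cannot be derived without an SD; it can only be solved backwards. The standardised difference detectable with 80% power at 0.05 is (1.960 + 0.842) × √(2/85) = 0.430 SD by the normal approximation, or 0.432 SD by the t-test. If the 15% is read as 15 units, the implied SD is 15/0.432 ≈ 34.7. Assumed SDs of 30, 35 and 40 would give 63, 86 and 112 per arm. If the sizing had used 0.025 per contrast, which the documents do not say, the detectable difference would be 0.477 SD. Both values are carried below as assumptions.

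**Family error with no true effect, each test at 0.05, any one counting.**
- Upper guide, independent tests: 1 − 0.95² = 9.75% for two tests; 1 − 0.95⁴ = 18.5% for four.
- The two contrasts share arm 1, so their test statistics correlate at 0.5. Simulation with that structure gives about 9% for one endpoint.
- For two endpoints it gives about 17% at endpoint correlation 0, 16% at 0.5 and 13% at 0.9.
- Results are the same at 85 or 76 per arm. Pain is counted as one score per patient. Section 7.3 has five assessment times, so testing each separately would enlarge the family.

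**Which contrast tests which feature.**

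| Contrast | Number of sutures | Position of angle knots | Named in the plan |
|---|---|---|---|
| 1 vs 2 | differs | same (above) | yes |
| 1 vs 3 | differs | differs | yes |
| 2 vs 3 | same | differs | no |

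**Error under a defined rule.** If the three-group test is run first and the three pairs are tested at the same alpha only when it is significant, the procedure is closed for three groups. Simulated family error is 5% at alpha 0.05.

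**Power for 1 vs 3 when only arm 3 differs, on both endpoints** (ranges: endpoint correlation 0 to 0.9; evaluable at 35% loss: 350 × 0.65 / 3 = 75.8, about 76 per arm):

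| Rule | 85 per arm, 0.432 SD | 85 per arm, 0.477 SD | 76 per arm, 0.432 SD | 76 per arm, 0.477 SD |
|---|---|---|---|---|
| One primary, 0.05 | 76% | 84% | 70% | 80% |
| Either of two, 0.025 each (per endpoint) | 66% | 76% | 60% | 70% |
| Both on the same contrast (Holm on the larger p) | 46–62% | 61–73% | 38–56% | 52–67% |

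**2 vs 3.** If arm 2 lies midway between arms 1 and 3, power at 85 per arm with one primary endpoint is 28% at 0.432 SD and 33% at 0.477 SD. The 95% confidence interval half-width is about 1.97 × √(2/85) ≈ 0.30 SD.

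**The case against.** **The promised SAP will settle it.** It may, and section 7.2 keeps the blind until after database lock, so there is time. But the text to be carried forward has an undivided 0.05 and no rule.

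**Pain may be the only primary endpoint.** The pain-only sizing and the singular wording in section 10.2 support this; the two lists in the synopsis contradict it. This stands: a reader might infer that two primary endpoints are settled and that 13–17% is the figure, but the documents do not settle it. With one primary endpoint the figure is about 9%.

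**The inflation assumes a rule that the plan does not state.** True. A reader might infer that the plan adopts an any-one-counts rule; it does not. The percentages show what the silence permits.

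**Comparing each two-suture method with arm 1 is a coherent design, and the general wording could include 2 vs 3.** The synopsis objectives, section 6 and section 10.2 do speak loosely of comparing the groups, and section 2.1 does not name the comparator for its further reduction. But where the plan lists pairs, 2 vs 3 is absent, and no other pair isolates knot position.

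**2 vs 3 is underpowered.** It is. A reader might also infer that adding it would settle a case where one listed contrast is significant and the other is not. The trial's size does not support that: a non-significant 2 vs 3 is the likely result even with a moderate true difference. This favours reporting it mainly as an estimate with an interval, not leaving it out.

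**Conclusion.** Both gaps are real and should be closed before unblinding. No rule links the primary tests to a claim of success, and the number of primary endpoints is inconsistent. If each test were run at 0.05 and any one counted, family error would be about 9% with one primary endpoint and 13–17% with two, given assumed endpoint correlations of 0.9 to 0 and one pain score per patient.

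The contrast that isolates burying the knot is not named, so the listed tests leave that hypothesis without a direct test. The data to estimate it will be collected, so this is a gap in the analysis plan and not in the design.

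The power figures rest on assumed differences of 0.432 and 0.477 SD, because no SD is given. At 0.432 SD all three rules fall below the stated 80%, and this holds at 85 and at 76 per arm.

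**What to change.** In section 10.2 and the synopsis, and fixed in the SAP before the blind is broken:

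1. Reconcile the synopsis, section 3.1 and section 10.2 on whether there is one primary endpoint or two. The choice is the sponsor's.
2. Add 2 vs 3. Report all three pairwise differences with 95% confidence intervals whatever the test results, and state that a non-significant 2 vs 3 is not evidence of no effect.
3. State the success rule. Within a primary endpoint, run the three-group test and, only if it is significant, test the three pairs at the same alpha. Use 0.05 for a single primary endpoint, or 0.025 for each endpoint if either of two may give success. If both endpoints must succeed on the same contrast, replace this with the larger of the two p-values for each contrast and apply Holm at 0.05 across the three contrasts. The three-group gate at 0.05 per endpoint is not safe for that last rule: when different pairs of arms are equal on the two endpoints, simulated error reached 9.8% for a large assumed effect (1.5 SD), against 5.0% at most with Holm.
4. Restate the power under the chosen rule, with the SD it assumes and at the number expected to be evaluable.

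The cost is wording and a less favourable power statement. At 0.432 SD and 85 per arm, the 80% becomes about 76%, 66% per endpoint, or 46–62%, depending on the rule; at about 76 evaluable per arm it becomes about 70%, 60% or 38–56%. No extra patients or visits are needed.

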#### 3.2 Secondary Objectives

Our secondary objective relates specifically to whether there is a difference in pain in patients undergoing primary or repeat caesarean sections. This will also be determined using sub-group analysis of participant pain scores based upon their questionnaire responses.

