#### 5.2 Sample Size

Our sample size is based upon a power of 80% at an alpha of 0.05 based on a two-sided t-test comparing groups. Based on these findings, our total sample size in each arm is 85 participants. In total, as there are three arms, our total sample size requires 255 participants, whereby randomising 85 participants to each group. In addition, we aim to undertake a sub-group analysis comparing primary to repeat Caesarean section with a power of 80% at an alpha of 0.05. Once again, a two-sided t-test would be used and based on these findings, we would require a total sample size of 140 participants, whereby comparing 70 participants per group. Given these minimum requirements and we estimate a drop-out rate of approximately 35%, we aim to recruit a total of 350 participants to this study.

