## 7 STUDY TREATMENTS

#### 7.1 Method of Assigning Subjects to Treatment Groups

Up to 350 eligible patients will be randomly assigned to one of the three intervention groups in a 1:1 ratio using an Excel-based computer-generated randomisation scheme.

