#### 7.3 Data collection method

Participants will be randomised to one of the three groups and will be provided a participant identification number on the day of their surgical procedure after consenting to proceed with the study. Subsequent to this, a chart review will be used to gather demographic information on participants, including age, gravida and para status, number of previous Caesarean sections, medical and surgical history, medication list, body mass index, and any obstetrical complications during the pregnancy. Participant's e-mails will be collected and saved in a separate document to maintain confidentiality.

Subsequent to this, participants will be e-mailed a link at each given time parameter to fill in their questionnaires which is a modified MD Anderson Brief Pain Inventory as a secure Google Docs Form (post-operative day #1 and 2, and at 2, 6 and 10 weeks post-operatively). As the participant's only identification is their participant identification number, this maintains participant confidentiality.

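### The primary-versus-repeat Caesarean comparison is observational, but only an unadjusted t-test is planned for it, although age, body mass index and obstetric complications are collected

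*Combined protocol and SAP*

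**What the plan says.** Section 3.2 sets one secondary objective: "whether there is a difference in pain in patients undergoing primary or repeat caesarean sections". Section 10.2 gives its only analysis. It opens "Specific to our subgroup analysis evaluating primary vs. repeat caesarean section, based upon an 80% power at an alpha of 0.05" and continues "we anticipate a 15% difference in comparing these two groups using a two-sided T-test". Section 5.2 gives the size: "we would require a total sample size of 140 participants, whereby comparing 70 participants per group". The synopsis expresses the same target as a "15% difference in pain scores".

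The randomised factor is closure method. Section 7.1 has patients "randomly assigned to one of the three intervention groups in a 1:1 ratio using an Excel-based computer-generated randomisation scheme" and mentions no stratification by primary or repeat status.

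Section 7.3 lists the chart-review variables, "including age, gravida and para status, number of previous Caesarean sections, medical and surgical history, medication list, body mass index", and then adds obstetrical complications of the pregnancy. Section 10.1 repeats most of the list, with height and weight in place of body mass index. Neither section, nor 10.2, assigns any of these variables to a model. No regression, covariate or closure-arm term is named anywhere. Section 10 says that a detailed SAP will be written before the final data are analysed and may modify the plan.

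**The concern.** Primary or repeat status is something a woman brings to the trial, so randomisation does not balance the two groups. They may differ in age, body mass index and complications of the current pregnancy, and any of these may be related to pain. An unadjusted comparison of means combines such differences with whatever is attached to primary/repeat status itself. The combined figure may show a difference where there is none after adjustment, or hide one that exists. Section 4.2 relies on randomisation to limit bias. That protection does not reach this contrast, and the limitations listed there do not say so.

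The label adds to the difficulty. The plan calls this a sub-group analysis, but the test described compares two kinds of patient. It does not ask whether the effect of closure method differs between them.

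**Working it through.** **1. The plan's own figure.** The stated inputs are two-sided alpha 0.05, 80% power, a 15% difference and 70 per group. No SD or reference mean is given, so 140 cannot be reproduced forwards. Solved backwards:

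- Normal approximation: d = (1.960 + 0.842) × √(2/70) = 0.474.
- Exact t-test: d = 0.477. If 15% is a relative difference, this implies SD/mean = 0.15/0.477 = 0.31.

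So 70 per group is sized to detect about 0.477 SD.

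**2. Bias from one unadjusted covariate.** Bias in SD of pain = imbalance in the covariate (SD) × its correlation with pain. Both inputs are assumed, because the documents give neither. The range used is 0.3 to 0.7 SD for imbalance and 0.2 to 0.3 for correlation.

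**3. Rejection rate when there is no covariate-adjusted difference.** This comes from the noncentral t with 138 degrees of freedom and noncentrality = bias × √(70 × 70/140) = bias × 5.916.

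| Imbalance | Correlation | Bias (SD) | Share of 0.477 | Noncentrality | Rejection rate |
|---|---|---|---|---|---|
| 0.3 | 0.2 | 0.06 | 13% | 0.355 | 6.4% |
| 0.3 | 0.3 | 0.09 | 19% | 0.532 | 8.3% |
| 0.5 | 0.2 | 0.10 | 21% | 0.592 | 9.0% |
| 0.5 | 0.3 | 0.15 | 31% | 0.887 | 14.3% |
| 0.7 | 0.2 | 0.14 | 29% | 0.828 | 13.0% |
| 0.7 | 0.3 | 0.21 | 44% | 1.242 | 23.5% |

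**4. Masking.** If the adjusted difference really is 0.477 SD and the bias runs the other way, noncentrality is (0.477 − bias) × 5.916. A bias of 0.06 gives 2.47 and power of about 69%. A bias of 0.21 gives 1.58 and power of about 35%. The nominal power is 80%.

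**5. Closure arm.** Closure is randomised independently of primary/repeat status, so its expected contribution to this contrast is zero. In 20,000 simulated comparisons at 70 v 70, with an effect of 0.43 SD in arms 2 and 3, mean bias was 0.00 SD, 95% of chance biases were below 0.07 SD, and the t-test rejected in 5.0%.

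**6. Price of adjusting.** With equal groups, the total needed is about 140 × (1 − correlation²) × (1 + imbalance²/4).

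- Lowest on the same range: 140 × 0.91 × 1.0225 = 130.3, so 131.
- Highest: 140 × 0.96 × 1.1225 = 150.9, so 151.

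The change from 140 is small in either direction, and section 5.2 plans to recruit 350.

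**The case against.** The strongest reply is that section 3.2 asks only whether pain differs between the two groups. For that descriptive question an unadjusted t-test tests the right hypothesis. If age or body mass index makes the group means differ, rejecting is correct. This stands. The rates in the table are not failures of the t-test. They are rejection rates against a covariate-adjusted hypothesis that the plan does not state. But the plan does not say that the contrast is descriptive either.

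A reader might infer that the trial means to report the result as an effect of repeat surgery. The documents do not support that: they speak of a difference and attribute it to nothing. A reader might also count closure arm among the confounders. It is not a systematic one, because it is randomised, and the t-test's error rate already covers chance imbalance.

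The size of any bias is unknown. At the low end of the assumed range the rejection rate is close to nominal. Higher rates can be produced by assuming larger or unequal groups, but the only size documented for this comparison is 70 v 70.

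Finally, a fuller SAP is promised. It is a proper route for the change, but the present text specifies no adjustment. Choosing covariates now avoids choosing them after the data have been seen.

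**Conclusion.** The point holds in this limited form: a powered test is planned on a non-randomised contrast, plausible confounders are collected and unused, and the text does not say how the result is to be read. The illustration of about 6% to 23% at 70 v 70, against a nominal 5%, rests entirely on the assumed imbalance and correlation and on a single covariate. It shows that the bias could matter, not that it does. It would be a mistake to conclude that the t-test is invalid in itself or that the randomised closure comparisons are affected. The matter concerns a secondary objective only. The change is still worth making, because the data are already collected and it costs little.

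**What to change.** In section 10.2, replace the t-test for this comparison with a pre-specified linear model of pain on primary/repeat status, with age, body mass index and current obstetric complications as covariates. Add closure arm as a term for precision, not to remove bias. Number of previous Caesarean sections defines the groups and cannot serve as a covariate.

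Report the adjusted difference with its 95% interval, described as an association, and give the unadjusted difference beside it. Adjustment deals only with measured covariates, so the wording should stay at association. Carry the same text into the promised SAP.

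In the synopsis and in sections 3.2, 5.2 and 10.2, call this a between-group comparison rather than a sub-group analysis.

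The cost is a few lines of text, a little more analysis work and a possible small change in precision (about 131 to 151 in total against 140, on the assumed range). No new data collection is needed.
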